# Barrier methods (each time the subject has intercourse) where applicable\*:

- Cap (plus spermicidal cream or jelly) PLUS male condom and spermicide
- Diaphragm (plus spermicidal cream or jelly) PLUS male condom and spermicide

#### Intrauterine devices (IUDs):

- Copper T PLUS condom or spermicide
- Progesterone T PLUS condom or spermicide

#### Hormonal contraceptives:

- Implants
- Hormone shot/injection
- Combined pill
- Minipill
- Patch
- Vaginal ring PLUS male condom and spermicide

\*Barrier methods is only applicable in countries where spermicide is commercially available.

Subjects will be provided with information on acceptable methods of contraception as part of the subject informed consent process and will be asked to sign a consent form stating that they understand the requirements for avoidance of pregnancy, donation of ova, and sperm donation during the course of the study.

During the course of the study, regular hCG pregnancy tests will be performed only for women of childbearing potential and subjects will receive continued guidance with respect to the avoidance of pregnancy and sperm donation as part of the study procedures (Appendix A). In addition to a negative serum and urine hCG pregnancy test at Screening, subjects also must have a negative urine hCG pregnancy test at Day -1.

## 9.1.12 Pregnancy

If any subject is found to be pregnant during the study she should be withdrawn and any sponsor-supplied drug (dexlansoprazole 30 mg capsules, matching placebo) should be discontinued immediately. In addition, any pregnancies in the partner of a man subject during the study or for 30 days after the last dose should be recorded following authorization from the subject's partner.

If the pregnancy occurs during administration of active study medication, eg, after Visit 2 or within 30 days of the last dose of active study medication, the pregnancy should be reported immediately, using a pregnancy notification form, to the contact listed in Section 1.0.

Dexlansoprazole Capsules	
Study No. TAK-390MR_302	Page 43 of 82
Protocol Incorporating Amendment No. 03	20 February 2017

Should the pregnancy occur during or after administration of blinded drug, the investigator must inform the subject of their right to receive treatment information. If the subject chooses to receive unblinded treatment information, the individual blind should be broken by the investigator. Subjects randomized to placebo need not be followed.

If the woman subject and/or woman partner of a man who is a subject agrees to the primary care physician being informed, the investigator should notify the primary care physician that the subject/woman partner of the subject was participating in a clinical study at the time she became pregnant and provide details of treatment the subject received (blinded or unblinded, as applicable).

All reported pregnancies will be followed up to final outcome, using the pregnancy form. The outcome, including any premature termination, must be reported to the sponsor. An evaluation after the birth of the child will also be conducted.

# 9.1.13 ECG

A standard 12-lead ECG will be recorded. The investigator (or a qualified observer at the investigational site) will interpret the ECG using 1 of the following categories: within normal limits, abnormal but not clinically significant, or abnormal and clinically significant.

The time that the ECG was performed will be recorded. The following parameters will be recorded on the eCRF from the subject's ECG tracing: heart rate, RR interval, PR interval, QT interval, and QRS interval.

As ECG tracings on thermal paper fade over time, any such tracings should be completely photocopied and both the original tracing and the counter-signed copy should be filed in the subject's medical record.

## 9.1.14 Documentation of Screen Failure

Investigators must account for all subjects who sign informed consent. If the subject is found to be not eligible at this visit, the investigator should complete the eCRF.

The IWRS should be contacted as a notification of screen failure.

The primary reason for screen failure is recorded in the eCRF using the following categories:

- Pretreatment event/AE.
- Did not meet inclusion criteria or did meet exclusion criteria.
- Significant protocol deviation.
- Lost to follow-up.
- Voluntary withdrawal.
- Study termination.
- Other.

Subject numbers assigned to subjects who fail screening should not be reused.

# 9.1.15 Documentation of Study Randomization

Only subjects who meet all of the inclusion criteria and none of the exclusion criteria are eligible for randomization into the Treatment Phase.

If the subject is found to be not eligible for randomization, the investigator should record the primary reason for failure on the applicable eCRF.

All screening procedures and test must be reviewed prior to randomization. Subjects who meet all the inclusion and none of the exclusion criteria will be randomized via IWRS.

Instructions on accessing and using the IWRS will be provided in a separate manual. Blinded details of subject treatment allocation (medication ID numbers) provided via the IWRS should be documented in the subject's medical record and/or eCRF.

# 9.1.16 Endoscopy

During Screening Visit an endoscopy will be performed on all subjects to document the presence/absence of EE. Endoscopy should be performed while subjects are fasted and according to the usual practice of the institution (ie, with regard to premedications or concomitant therapies, as long as they are not prohibited in Section 1 of this protocol). Subjects with macroscopic normal esophagus will be eligible for the study.

The screening endoscopy must be performed within 14 days prior to randomization. Any reliable, documented results available from an endoscopy performed in a routine clinical setting (before signing of informed consent) in the same institution will be accepted, given the invasive nature of the procedure.

Any subjects with suspicious Barrett's esophagus seen during screening endoscopy will be excluded from the study. These Endoscopy assessments will be recorded on the eCRF and a copy of the results should be kept with the subject's notes. Digital images of the endoscopy should be captured and stored at the investigational site; images may be accessed by Takeda as necessary for quality assurance purpose.

# 9.2 Monitoring Subject Treatment Compliance

Subjects will be required to bring study medication containers and unused medications to each dispensing site visit and final visit. Investigators or designee should perform subject treatment compliance checks by reviewing the subject's eDiary and returned medications.

If a subject is persistently noncompliant with the study medication [dexlansoprazole 30 mg capsules or placebo] (eg, at more than 2 consecutive compliance checks to have taken less than 80% or more than 120% of the study medication), the subject should be withdrawn from the study. At each applicable study visit it should be documented in the subject's medical record that study medication was dispensed or collected, and/or checked for compliance. All subjects should be

reinstructed about the dosing requirement during study contacts. The authorized study personnel conducting the re-education must document the process in the subject source records.

When rescue medication has been taken for more than 7 consecutive days during the study Treatment Period, the investigator should discuss with CRO/sponsor and decide whether to withdraw the subject.

# 9.3 Schedule of Observations and Procedures

The schedule for all study-related procedures for all evaluations is shown in Appendix A.

# 9.3.1 Screening

Subjects will be screened within 21 days prior to randomization. Subjects will be screened in accordance with predefined inclusion and exclusion criteria as described in Section 7.0. See Sections 9.1.14 for procedures for screening failures.

The clinical laboratory tests, hepatitis panel and endoscopy must be performed within 14 days prior to randomization.

Any reliable, documented results available from an endoscopy performed in a routine clinical setting (before signing of informed consent) in the same institution will be accepted, given the invasive nature of the procedure.

# Procedures to be Completed During the Screening Period (Days -21 to Day -2) include:

- Informed consent.
- Demographics, medical and social history.
- Medication history.
- Physical examination.
- Vital signs.
- Weight and height.
- Concomitant medication(s).
- Concurrent medical condition(s).
- Pretreatment events assessment.
- Prescribe rescue medication and give the medical instruction, as necessary.
- Screening clinical laboratory tests and hematology (to be performed within 14 days prior to randomization).
- Urinalysis.
- Serum and urine hCG (women of child-bearing potential only).
- FSH (only performed if menopause is suspected).

- Guidance on the avoidance of pregnancy.
- Instructions on how to make entries in the subject eDiary, provision of the eDiary, and commencement of eDiary entry.
- ECG.
- Hepatitis panel including: HBsAg and HCV-antibody (to be performed within 14 days prior to randomization).
- Endoscopy (to be performed within 14 days prior to randomization)

#### 9.3.2 Study Randomization

If the subject has satisfied all of the inclusion criteria and none of the exclusion criteria for randomization, the subject should be randomized using the IWRS system, as described in Section 8.2. Subjects will be instructed when to take the first dose of investigational drug as described in Section 6.1. The procedure for documenting Screening failures is provided in Section 9.1.14.

#### 9.3.2.1 Day -1

- Physical exam.
- Vitals signs.
- Weight.
- Clinical laboratory tests (subjects should be fasting for a minimum of 8 hours prior to all labs) to include:
  - Urine and serum pregnancy test (baseline serum pregnancy test will not be needed if the screening pregnancy test is within 14 days of randomization).
  - Fasting gastrin.
- GERD symptoms investigator assessment.
- Daily eDiary review including compliance check.
- Concomitant medication(s).
- Pretreatment events assessment.
- IWRS randomization.
- Dispense study medication via IWRS.
- Rescue medication compliance and accountability.
- Dispense rescue medication as needed.

#### 9.3.3 Treatment Period

#### 9.3.3.1 Day 1

- Begin study medication.
- Complete daily eDiary.

## 9.3.3.2 Week 2 Visit (± 3Days)

Procedures to be completed at Week 2 Visit include:

- Physical examination.
- GERD symptoms investigator assessment.
- Vital signs.
- Weight.
- AE assessment.
- Concomitant medication(s).
- Daily eDiary review and compliance check.
- Study drug compliance and accountability.
- Rescue medication compliance and accountability.
- Dispense study medication via IWRS.

## 9.3.4 Final Visit or Early Termination (± 3 Days)

Procedures to be completed at Week 4/Final Visit include:

- Physical examination.
- GERD symptoms investigator assessment.
- Vital signs.
- Weight.
- AE assessment.
- Concomitant medication(s).
- Clinical laboratory tests (subjects should be fasting for a minimum of 8 hours prior to all labs) to include:
  - Chemistry panel and hematology.
  - Serum and urine hCG.
  - Urinalysis.

- Fasting gastrin.
- ECG.
- Daily eDiary review.
- Return of study medication.
- Study drug compliance and accountability.
- Rescue medication compliance and accountability.

For all subjects receiving study medication, the investigator must complete the End of Study eCRF page.

## 9.3.5 Unscheduled Visit

An unscheduled visit may occur when the subject returns to the clinic at any time during the Treatment Period of the study for the evaluation of symptoms or side effects.

At minimum, the following procedures are to be completed with additional procedures at the investigator's discretion:

- Physical examination.
- GERD symptoms investigator assessment.
- Vital signs.
- Weight.
- AE assessment.
- Fasting gastrin.
- Concomitant medication(s).

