During this 4-week Treatment Period, study drug will be self-administered, orally, once a day, in the morning, without regard to food. Subjects will continue to document the presence and maximum severity of daytime and nighttime heartburn symptoms and record usage of rescue medication using an eDiary. Subject visits will be conducted at Weeks 2 and 4 of the Treatment Period to collect and/or dispense study drug, assess GERD symptoms, review concomitant medication use, assess adverse events and subject will undergo a physical examination including vital signs. In addition, at the Week 4/ Final Visit, all subjects will undergo laboratory evaluations, ECG, fasting serum gastrin and urine pregnancy test (all women of childbearing potential). Subjects who prematurely discontinue during the study after the randomization should undergo Week 4/Final Visit procedures no later than 5 days after the last dose of study drug.

A schematic of the study design is included as Figure 6.a. A schedule of assessments is listed in Appendix A.

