5.2.5 Definition of Study Days and Visit Window

Study day was calculated relative to the date of the first dose of study drug in the study. The study day prior to the first dose of study drug was calculated as:

$$\text{Date of assessment/event} - \text{date of first dose of study drug}$$

The study day on or after the first dose of study drug was calculated as:

$$\text{Date of assessment/event} - \text{date of first dose of study drug} + 1.$$

The visit windows for the post baseline visits were defined in [Table 5.a](#). If a subject had more than 1 measurement in the same visit window, the measurement closest to the scheduled visit was used. If 2 measurements in the same window were of equal distance to the scheduled visit, the measurement that occurred after the scheduled visit was used. If 2 or more measurements occurred on the same day, the last value obtained was used.

Table 5.a Visit Window

Visit	Scheduled Day	Safety Labs & Serum Gastrin	Vital Signs	ECG	GERD Symptoms Investigator Assessment
Baseline	Day -1	≤1	≤1	≤1	≤1
Week 2	Day 14	2-21	2-21	NA	2-21
Week 4	Day 28	22-35	22-35	2-35	22-35

Note: Safety labs (including gastrin), vital signs, and ECG data obtained more than 7 days after the last day of study drug and efficacy data obtained more than 7 days after the last day of study drug weren’t included in the analyses.

Diary entries were assigned to study days according to the beginning of the recall period. Specifically, entries completed in the evening (reporting heartburn during the day) were assigned

to the same day; entries completed in the morning (reporting heartburn during the night) were assigned to the previous day.

For the purpose of diary compliance calculation and derivation of diary-based endpoints, the last day of study drug wasn't included since the subject was not expected to have completed the diary entries for that day by the Week 4/Final Visit. Therefore, summaries for the 4 weeks of treatment included Study Day 1 through Study Day 35 or the day before the last dose of study drug, whichever occurred first.

For efficacy variables summarized by visit, the value closest to the last day of study drug was summarized for each subject, including those within 7 days of the last day of study drug. If 2 measurements were of equal distance to the last day of study drug, the later measurement was used.

AEs that started more than 30 days after the last dose of study drug were listed, but excluded from the summaries and analyses.

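### The SAP visit windows do not exclude unscheduled, symptom-prompted assessments, so such a score can replace an early Week 2 GERD severity score or fill a missed visit

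*Protocol*

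**What the plan says.** **Trigger and content.** Protocol Section 9.3.5 lets a subject return "at any time during the Treatment Period of the study for the evaluation of symptoms or side effects". It then sets a required list, introduced by "At minimum, the following procedures are to be completed with additional procedures at the investigator's discretion", which includes the investigator GERD assessment and fasting gastrin. Appendix A marks both in the Unscheduled Visit column.

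**Schedule.** Protocol Section 6.1 states: "Subject visits will be conducted at Weeks 2 and 4 of the Treatment Period". Sections 9.3.3.2 and 9.3.4 allow ±3 days for each. The GERD assessment is listed at both visits. On-treatment gastrin is scheduled only at Week 4/Final.

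**Assignment to visits.** Table 5.a in SAP Section 5.2.5 gives Week 2 a scheduled day of 14 and a window of Days 2-21. Week 4 has a scheduled day of 28 and a window of Days 22-35. The same windows serve the GERD assessment and serum gastrin. Two selection rules follow:

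- Closest day: "If a subject had more than 1 measurement in the same visit window, the measurement closest to the scheduled visit was used". In a tie, "the measurement that occurred after the scheduled visit was used".
- Closest to last dose, for efficacy variables summarized by visit: "the value closest to the last day of study drug was summarized for each subject".

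The SAP does not say how the two rules fit together. Neither rule mentions visit type.

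**The concern.** If a subject comes in because symptoms have worsened, the timing of the severity score depends on the outcome being scored. Allowing that score to displace one taken on schedule means the Week 2 value is no longer measured at a time fixed independently of how the subject feels.

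The endpoint exposed is investigator-assessed GERD severity at Weeks 2 and 4, an additional efficacy endpoint. It matters somewhat more than its rank suggests. The primary and secondary comparisons were not significant (p=0.057 and p=0.268), and the conclusion in SAP Section 9.2 goes on to cite the investigator-assessed symptoms.

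For gastrin the matter is descriptive: a Week 2 window exists with no planned sample to fill it.

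**Working it through.** No reported figure can be recomputed to test this, because the documents do not count unscheduled visits. The check is therefore an enumeration of which days can displace which.

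**Inputs.** Target days 14 and 28 and windows 2-21 and 22-35 (SAP Table 5.a). Scheduled visits on Days 11-17 and 25-31 (Protocol ±3 days). The GERD score is the maximum severity over the 7 days before the visit (Protocol Section 9.1.6). The last dose is taken the day before the Final Visit (Protocol Section 8.1.3).

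**Closest-day rule, Week 2.** The value with the smaller distance |day − 14| wins; ties go to the later value. Example: visit on Day 11, walk-in on Day 13. The distances are |11 − 14| = 3 and |13 − 14| = 1, so the walk-in is used.

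| Week 2 visit | Walk-in days that win | Days recalled at the scheduled visit |
|---|---|---|
| Day 11 | 12-17 | 4-10 |
| Day 12 | 13-16 | 5-11 |
| Day 13 | 14-15 | 6-12 |
| Day 14 | none | 7-13 |
| Day 15 | 14 | 8-14 |
| Day 16 | 13-15 | 9-15 |
| Day 17 | 12-16 | 10-16 |

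For visits on Days 15-17, every winning walk-in day lies inside the scheduled visit's own recall period, so the scheduled score should reflect the same flare. For visits on Days 11-13, every winning walk-in comes after the scheduled visit, and its flare can lie outside that visit's recall. That is where an outcome-prompted score can differ systematically from the one it replaces.

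**Closest-day rule, Week 4.** The comparison is |day − 28|, with the walk-in before the Final Visit.

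| Final Visit | Walk-in days that win | Days recalled at the Final Visit |
|---|---|---|
| Days 25-28 | none | not needed |
| Day 29 | 28 | 22-28 |
| Day 30 | 27-29 | 23-29 |
| Day 31 | 26-30 | 24-30 |

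Replacement needs a Final Visit on Day 29 or later, and the recall period then contains the walk-in day each time.

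**Closest-to-last-dose rule, if applied within windows.** At Week 2, any walk-in after the scheduled visit and up to Day 21 is nearer the last dose of a completed course, so it wins even over a Day 14 visit. At Week 4, a walk-in wins only on the last dosing day (distance 0 against 1 for the Final Visit), which is again inside the Final Visit's recall.

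**Missed visits.** Under either rule, a walk-in that is the only value in a window becomes the visit value. SAP Table 6.a bounds this route. Of 217 randomized, 2 were not treated, leaving 215; 205 completed all planned visits, so 215 − 205 = 10 treated subjects did not.

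**Gastrin.** With no scheduled Week 2 sample, nothing is displaced there; only unscheduled or early-termination samples can occupy that window. SAP Table 8.c reports Week 4 only, on 102 placebo and 103 dexlansoprazole subjects. Its percentages reproduce: 6/102 = 5.9%, 3/102 = 2.9%, 15/103 = 14.6%, 4/103 = 3.9%. The denominators equal the numbers completing all visits, which does not show whether any value was substituted.

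**The case against.** The strongest reply is the 7-day maximum recall. A scheduled visit shortly after a walk-in covers the same bad days, so swapping one score for the other should change little. This stands for late Week 2 visits and for Week 4. It does not help when the walk-in follows an early Week 2 visit.

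The closest-to-last-dose rule can also be cited as protective. It keeps a Day 17 score over a Day 13 walk-in, and a Day 31 score over a Day 27 walk-in (last dose Day 30: distances 1 and 3). That is correct, but within windows the same rule opens the Week 2 value to every later walk-in up to Day 21.

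The phrase about the scheduled visit might mean the actual protocol visit, which would then always win under the closest-day rule. The Scheduled Day column of Table 5.a points the other way, and the text does not settle it.

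A reader might infer that unscheduled gastrin samples are non-fasting. The protocol asks for a fasting sample in Section 9.3.5, in note (b) to Table 9.a and in note (d) to Appendix A. A non-fasted sample would be a deviation, not a gap in the plan.

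Finally, the exposed endpoint is additional and the missed-visit route is limited to about 10 treated subjects. Both points stand and keep this minor.

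**Conclusion.** The gap is real but small. The SAP as written lets a symptom-prompted score replace the score from a Week 2 visit on Days 11-13 (or any Week 2 visit, if the last-dose rule works within windows) and lets it fill a missed visit. At Week 4 the effect should be minimal. It is not strictly nil, since a walk-in's own recall reaches further back than the Final Visit's. The eDiary primary and secondary endpoints are untouched.

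Two stronger inferences are tempting and unsupported:

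- **That the rule favours dexlansoprazole or inflates the false-positive rate by a known amount.** Without counts of unscheduled visits by arm, any such figure would rest on invented replacement rates and score shifts. The direction is not established either: side effects also trigger these visits, and treatment-emergent events were reported in 36.4% on dexlansoprazole and 32.4% on placebo.
- **That the borderline Week 4 belching result (p=0.042) is put in doubt.** It is a Week 4 result, where the mechanism largely disappears. The reported significant Week 2 result is heartburn (p=0.009), and the conclusion in SAP Section 9.2 refers to symptoms after 4 weeks.

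The finding assumes that the scheduled visit means the Table 5.a day, that unscheduled scores enter the windowed data, and that walk-ins precede a Final Visit held the day after the last dose.

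**What to change.** In SAP Section 5.2.5, state that by-visit GERD severity and gastrin summaries use only the scheduled Week 2 and Week 4/Final or Early Termination assessments, and that unscheduled assessments are listed separately. The same passage should say which selection rule governs within a window, because an Early Termination visit up to Day 21 can still share the window with a Week 2 visit.

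Since results are already reported, rerun the GERD severity analysis with this filter and confirm that the reported results are unchanged. A count of unscheduled visits by arm and week would show whether the point ever applied.

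The cost is a sentence or two, a visit-type filter and one rerun. The downside is that a subject who misses a scheduled visit has no substitute value. With 205 of 215 treated subjects completing all planned visits, that loss is small.
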